**Each sleep study night will consist of the following procedures:**

*Pre-sleep procedures.* Subjects will undergo a history and physical examination. They will report to the CRU at 4:00 PM and undergo anthropometric assessment including weight, height, neck, and waist circumference. At 5:30 PM, they will eat a standard dinner containing 30% fat, 50% carbohydrate, and 20% protein with kcal based upon the Mifflin-St Jeor formula. Two peripheral IVs (18 to 20 gauge) will be placed. All samples are obtained through the IV without disturbing the subject during sleep. Blood pressure will be checked at 6:30 PM, before administration of study drug. If systolic blood pressure is <90 or the heart rate is <50 then no drug will be administered. (In the event that this occurs, the study will still proceed so that CPAP and OSA nights can be compared and analyzed as a "no drug" group.) If blood pressure and heart rate are acceptable, propranolol LA 80 mg, or placebo (random order, crossover on study night 2 and 3) will be given. Participants and the investigators will be blinded to drug assignment.

*PSG setup.* On each study night from 10:30 PM until 6:30 AM, a PSG will be performed. The sleep study will include electroencephalography, electrooculography, oxygenation, respiratory effort, CPAP airflow, and transcutaneous CO2 monitoring. Respiratory effort will be measured by thoraco-abdominal movement assessed by mercury strain gauges. Surface electrodes will be placed at C3A2 and C3O1, a submental electrode, and left and right electro-oculogram will be used to stage sleep. Electrocardiograph (EKG) tracings will be recorded from three chest electrodes. Continuous measurement of oxygen saturation will be recorded using an ear oximeter (model No 472-1A, Hewlett Packard, Waltham, Mass). Transcutaneous CO2 will be monitored using a Radiometer TCM-4 device. Signals from the electroencephalograph, EKG, electromyogram, electrooculogram, respiratory strain gauge, ear oximeter and thermistors will be recorded on a computer with RemLogic software.

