*Respiratory interventions.* During the CPAP night, patients will sleep using CPAP set to their prescribed home CPAP settings. Airflow will be recorded with a pneumotachograph in the CPAP circuit. CPAP will be titrated if necessary to prevent obstructive hypopneas and apneas. During NDS nights, ClearPassage® strips will be applied at bedtime. Flow will be measured using a nasal cannula and oral thermistor. Sleep and respiratory events will be scored according to AASM criteria. Apneas will be considered present when there is no air flow for >10 seconds. Obstructive apneas will be considered present when apneas are associated with positive strain gauge deflections indicating thoracic movement. Apneas will be considered central in origin when cessation of air flow is not accompanied by thoracic movement as measured by the strain gauge. Mixed apneas will be defined by episodes of no air movement resulting from central apnea followed by obstruction. Hypopneas will be scored for reductions in airflow of 30% lasting >10 seconds accompanied by either an arousal or fall in oxyhemoglobin saturation of 3% or greater. Blood pressure is measured at 7 PM, 10:30 PM, and upon awakening after the morning blood sample at 6:30 AM.

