**d. Early stopping rules.**

At any point in the study, the subject may decline to participate. Indications for stopping are the development of severe adverse events. The IRB will be informed of any adverse events. Any serious adverse events will result in study discontinuation.

If propranolol has not yet been administered, and systolic BP  $<90$  or HR  $<50$  the study will continue without giving propranolol. The P.I. should be notified of this occurrence. If propranolol has been administered, and systolic BP  $<90$  or HR  $<50$  the study will be stopped early. The subject will be awoken from sleep to assess symptoms, hemodynamics, and orthostasis. The P.I. is to be notified for severe nocturnal hypoxemia with SpO2 consistently  $<85\%$  for  $>5$  min, or unstable cardiac arrhythmia on EKG during sleep.

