Sample size: In a preliminary study (n=6), Median individual heart rate during sleep \pm (SD) was 62.2 (9.2) with [OSA+placebo] and this decreased by 6.7 BPM with [OSA+propranolol]. To detect a 10% difference (reduction of 6.2 beats/min) at a power of 80% at a significance threshold of 0.05, using a one-tailed comparison, yields a sample size of 16 participants. Since we have already enrolled 5 subjects, we require 11 additional subjects. Assuming 20% dropout, we will enroll 14 additional subjects, a total of 19 participants.

Primary outcome: Median of continuously measured heart rate during sleep.

Secondary outcomes:

- augmentation index (normalized to 75 beats/min),
- heart rate variability metrics (HR standard deviation, min/max, 5th or 95th percentile)
- OSA severity (AHI, oximetry, event duration)
- sleep architecture (percent of each sleep stage during the night)
- Blood pressure
- metabolism (FFA, glucose, insulin).

Blinding:

As this is a double-blind study, above metrics will be calculated for each visit with only knowledge of visit number and not drug/placebo assignment. After these parameters have been derived, the research pharmacy will un-blind the biostatistician ([name]) and PI ([name]) to drug arm assignment to apply appropriate statistical tests, as described below.

Analysis:

For the primary analysis, we will derive summary metrics per night, per participant (i.e. median HR per night). Median heart rate per night will be compared between drug and placebo nights in a paired framework using paired student's T tests. Similar methods will be used to compare secondary outcomes. Some metrics will require additional derivation. For example, heart rate variation will be expressed as coefficients of variation, min/max and lower (5th) and upper (95th) percentiles, and visualized with Poincare plots as performed by collaborators at Johns Hopkins ².

Exploratory Analyses:

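### The stop at heart rate below 50 should shorten propranolol nights more often than placebo nights, and the SAP compares per-night HR SD and min/max without equalising recording length

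*SAP*

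**What the plan says.** The SAP's list of secondary outcomes includes "heart rate variability metrics (HR standard deviation, min/max, 5th or 95th percentile". Its Analysis paragraph adds that "heart rate variation will be expressed as coefficients of variation, min/max and lower (5th) and upper (95th) percentiles". Each metric is a single summary per participant per night. The primary outcome is tested by paired t-test, and "Similar methods will be used to compare secondary outcomes".

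Protocol 7d says that once the capsule has been given, a systolic pressure below 90 or a heart rate below 50 means that "the study will be stopped early. The subject will be awoken from sleep to assess symptoms, hemodynamics, and orthostasis". It gives no duration for the low heart rate. The text names propranolol only, but participants and investigators are blinded (Protocol 4, pre-sleep procedures and item c), so in practice the rule has to apply on both capsule nights. During sleep the trigger that can operate is heart rate, because "Blood pressure is measured at 7 PM, 10:30 PM, and upon awakening after the morning blood sample at 6:30 AM". Before dosing, "If systolic blood pressure is <90 or the heart rate is <50 then no drug will be administered", and exclusion criterion 1e sets the same limits at screening. A participant with a rate of 50 can therefore be enrolled and dosed.

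For the expected level, the SAP's sample size paragraph says that median sleeping heart rate in six pilot participants "was 62.2 (9.2) with [OSA+placebo] and this decreased by 6.7 BPM with [OSA+propranolol".

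Neither document sets a common recording window, a minimum length or a rule for stopped nights. The reasons for a repeat study under Protocol 4, post-test procedures, do not include a safety stop.

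**The concern.** The stop acts on heart rate, which is what the drug lowers, so it should cut short more propranolol nights than placebo nights. Blinding does not prevent this. SD, minimum and maximum depend on how much of the night was recorded. A longer record can only raise the maximum and lower the minimum, and where heart rate drifts slowly it also gives a larger SD.

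Comparing a short propranolol record with a full placebo record therefore produces a lower SD and a lower maximum whatever the drug does to variability. That would be read as sympathetic blunting, which is the trial's hypothesis. The minimum errs the other way: the record ends just as the rate gets low, so the drug's lowering of the minimum is understated, and that bears on safety.

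**Working it through.** **1. The plan's own figure.** Paired t-test, one-sided 0.05, difference 6.2, SD 9.2: the effect is 6.2/9.2 = 0.674, and n = 16 gives power 0.823. Dropout: 11/0.8 = 13.75, so 14, and 5 + 14 = 19. The SAP's 16 and 19 reproduce. The point here does not depend on them.

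**2. Which nights stop.** Expected propranolol level: 62.2 − 6.7 = 55.5. Margin above the stop: 62.2 − 50 = 12.2 bpm on placebo and 55.5 − 50 = 5.5 bpm on propranolol. With normal nightly medians and SD 9.2, P(median < 50) = Φ((50 − m)/9.2):
- placebo: Φ(−1.33), about 9%
- propranolol: Φ(−0.60), about 27%

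These are not stop rates. A night with a median above 50 can still be stopped, and the entry limits remove some low rates. They show only which arm is stopped more often.

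**3. False findings for SD.** Heart rate was simulated over 480 minutes (10:30 PM to 6:30 AM) with n = 19, the entry limits applied, the stop applied on both nights, a 6.7 bpm shift on propranolol and *no* drug effect on variability. The following were assumed, because the documents do not give them:
- between-person SD 9.2 or 6
- between-night correlation 0.5 or 0.8
- within-night SD 2 to 5 bpm
- correlation time 10 to 90 min (not every value in every setting)
- waking rate equal to the sleeping rate or 10 bpm above it

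The test was a paired t-test at two-sided 0.05, so a false finding of lower SD should occur in 2.5% of trials.

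| Time HR averages below 50 before the stop | False lower SD, shortened nights kept |
|---|---|
| 120 min | 1 to 16% |
| 30 min, drug effect rising gradually | 8 to 24% |
| 30 min, full drug effect from lights out | 13 to 46% |
| 5 min, records of any length used | 27 to 78% |
| 5 min, at least 30 min required on both nights | 2 to 25% |
| Same window on both nights | 0 to 4% |

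With a flat drug effect, stops on propranolol versus placebo nights ran 33–63% versus 6–32% (30 min) and 27–43% versus 3–19% (120 min).

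One setting in full: between-person SD 9.2, correlation 0.8, within-night SD 3, correlation time 40 min, 30-min trigger. Stops were 46% versus 19%, the SD difference was −0.27 bpm, and false lower SD was 26%. With matched windows it was 2.3%.

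**4. Minimum and maximum.** A second model used 30-second epochs, within-night SD mainly 3 or 5, correlation time mainly 2 or 20 min, triggers of 0.5 to 30 min, and pairs kept if both records reached 30 min. The true shift is 6.7 bpm for both metrics. The recorded maximum fell by 7.0 to 8.5 and the recorded minimum by 4.7 to 6.4. SD fell by 0.02 to 0.44 bpm, about 1 to 9%, and least when fluctuations were fast. Cutting both nights to their common length brought the SD difference to between −0.03 and +0.06 bpm, and the difference in range (maximum minus minimum) to between −0.01 and +0.31 bpm.

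**5. Coefficient of variation.** With SD unchanged, the lower mean alone multiplies CV by 62.2/55.5 = 1.12, a rise of about 12%. That offsets the shrinkage from a short record. False lower CV was 0 to 5% at 30- and 120-minute triggers.

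**The case against.** **Stopped nights may not enter the analysis.** The documents do not say that they are kept. A very short night might be repeated for low sleep efficiency or incomplete blood collection, or counted within the 20% dropout. If so, this mechanism does not arise. That stands as a condition on the point. Still, a safety stop is not a listed reason for repeat, and a summary per night, with no exclusion stated, implies that the night is used.

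**The strict triggers are doubtful.** A 5-minute trigger would stop 39 to 78% of propranolol nights, and the SAP's account of its six-person pilot mentions no such losses. A reader might take the 27 to 78% in the table as the expected error rate. The documents do not support that: it requires computing an SD from records only minutes long, and it falls to 2 to 25% once 30 minutes are required on both nights.

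**The flat drug effect is unfavourable to the plan.** Protocol 6a cites a gradual rise to a peak about 6 hours after dosing, which is about 1 AM for a 7 PM dose. With a gradual rise, the 30-minute range drops to 8 to 24%. This stands, and it is why the range is wide.

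**Dose adjustment could reduce stops.** Protocol 4c and 7c allow it, and it was not modelled. The expected mean fall of 6.7/62.2 = 10.8% lies inside the 15% limit, so the average effect would not trigger it.

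**HR variability as a whole is not shown to fall falsely.** The SAP's Analysis paragraph names CV, and CV is largely protected. This stands. The protection is an offset of two distortions, and SD and min/max remain listed outcomes.

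**Conclusion.** The point holds for HR SD, minimum and maximum, if shortened nights are kept. SD and maximum are biased downwards on propranolol, and the fall in the minimum is understated. The direction follows from the protocol's rule and the SAP's own heart rates.

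The size cannot be fixed from the documents, because the rule has no duration and no stops are counted. False lower SD runs from about nominal to 16% for a stop after 120 minutes below 50, and from about 8 to 46% for a stop after 30 minutes. Where a trial falls in these ranges depends on within-night variability and the timing of the drug effect.

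Two stronger inferences are not supported. One is that every variability metric would falsely fall: CV does not, at the 30- and 120-minute triggers. The other is that the primary result is inflated. The primary is given as "Primary outcome: Median of continuously measured heart rate during sleep", and in simulation its difference moved little: 5.4 to 6.3 bpm with gradual absorption, and about 5.9 to 7.05 in the second model, against a true 6.7. The primary median is not part of this point.

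Only secondary outcomes are affected, so this is a change worth considering rather than a defect in the trial's main comparison.

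**What to change.** Leave the safety rule and the primary median as they are. Before unblinding, add to the SAP:

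1. As the main analysis of these metrics, compute HR SD, CV, min/max and 5th/95th percentiles over the same elapsed time from lights out on both nights of a pair, ending at the earlier stop.
2. Do not silently drop pairs with a very short common window. Report how many there are and show results with and without them. Under a 5-minute trigger, a 30-minute minimum drops about 24 to 43% of pairs. These are the participants with the lowest rates, and their loss shrinks the min/max differences to about 5.2 to 6.4 bpm against a true 6.7.
3. Report stops and stop times by arm, and flag the minimum of a stopped night as censored below 50.

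The cost is one paragraph and no new data. The SAP already derives the metrics with only the visit number known, so the windows can be set blind. The downside is that part of the longer night goes unused, and in pairs with an early stop the metrics describe only early sleep, before peak drug effect.

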**Study overview:** There are a total of 4 study visits. The first visit is a consent, screening, and randomization visit. After consent, a screening EKG will be performed to exclude rhythm or conduction abnormalities and a urine pregnancy test to exclude pregnancy in potentially pregnant females. (If the participant has had a clinical EKG or EKG report in the last year that does not indicate any conduction disorders listed in the exclusion criteria, the screening EKG may be deferred.) A point of care screening test for hemoglobin will also be performed to exclude pre-existing anemia. Patients with a hemoglobin < 10 g/dL are ineligible for this study. They will be provided with ClearPassage® NDS to use at home during CPAP withdrawal nights.

Thereafter, there are 3 overnight visits to the CRU in random order. This protocol compares nocturnal metabolism in treated OSA (CPAP), untreated OSA (NDS), and beta-blocked OSA (NDS) in the same subject. OSA nights are performed in the lab after using NDS instead of CPAP for 2 nights at home.

**Covid-19 screening:** We will screen participants before their arrival for their each sleep study with a Covid-19 test. A negative screen within 72 hours of the CPAP visit will be needed prior to admission for the CPAP study visit.

During each OSA visit, propranolol or placebo is taken in the evening, in random order. Frequent blood sampling is performed throughout the visit. In the morning, DEXA (only 1 DEXA needed for entire study) is performed. We are targeting 1 week between visits, but will allow flexibility in scheduling patients unable to schedule 3 consecutive visits exactly 1 week apart; in this scenario we will allow a duration of  $\geq$  4 days or  $\leq$  3 weeks between visits. Each visit we will also administer stable isotopes to measure detailed lipid metabolism.

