Propranolol for Sleep Apnea Treatment (PROSAT)

NCT03049306

April 25, 2023

PROPRANOLOL FOR SLEEP APNEA THERAPY (PROSAT)

STATISTICAL PLAN

April 25, 2023

Developed by:

[figure not shown]
[figure not shown]
[name], Division of Pulmonary and Critical Care Medicine

[name], Johns Hopkins School of Public Health

Background:

20 million adults in the United States and >100 million adults worldwide have OSA, and the prevalence continues to rise with obesity. These figures are especially alarming as OSA is associated with cardiovascular disease and mortality. However, mechanisms linking OSA to these outcomes are unclear. As a result of this knowledge gap, fundamental questions such as what features of OSA are most harmful, and which patients can safely decline treatment, cannot be answered. Moreover, therapies for OSA such as CPAP are poorly tolerated, leaving non-adherent patients susceptible to CVD. We have observed that OSA acutely elevates nocturnal heart rate, morning blood pressure, and morning augmentation index (AIX)¹. These short-term changes may foster progression of cardiovascular disease if they recur on a chronic basis. In other contexts, these cardiovascular changes are induced by sympathetic nervous system activation. Therefore, we hypothesize that catecholamine release during sleep leads to increased heart rate, blood pressure, AIX, and altered metabolism. In this project we will examine whether OSA-related cardiometabolic changes during sleep can be prevented by beta blockade.

Design: Double-blind, crossover RCT of Propranolol LA vs. Placebo taken before sleep in patients with moderate-severe OSA. Participants will be CPAP-adherent patients who will temporarily discontinue CPAP for 3 nights prior to each visit, approximately 1 week apart. During sleep we will collect a full sleep study (oximetry, sleep staging, respiratory flow, muscle movements), IV blood samples (every 30 min). In the morning following each study, participants will undergo vascular assessment (endoPAT testing).

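### The primary paired t-test and the mixed models leave out visit order although drug order is randomised, which costs some power and lets a realised imbalance shift the estimate in either direction

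*SAP*

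**What the plan says.** The SAP (Design) describes a "Double-blind, crossover RCT of Propranolol LA vs. Placebo taken before sleep". Under its outcome and Analysis paragraphs the endpoint is "Primary outcome: Median of continuously measured heart rate during sleep", one value per night, "compared between drug and placebo nights in a paired framework" by paired t-tests. Secondary outcomes are to be handled in a similar way. The sample size is set "at a significance threshold of 0.05, using a one-tailed comparison".

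The SAP's mixed models (Exploratory Analyses) contain drug, subject and time. Time there means the course within a night, in 30-minute bins. The protocol's models (Data Analysis and Anticipated Outcomes; section 7, Study Statistics) contain condition or group, subject and, in the first of these places, time. None contains visit number, period or sequence.

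On order, the protocol's Study overview (section 4) says "Thereafter, there are 3 overnight visits to the CRU in random order" and "During each OSA visit, propranolol or placebo is taken in the evening, in random order". The pre-sleep procedures in the same section say "random order, crossover on study night 2 and 3". Neither document says how the order is generated or whether sequences are balanced. The SAP (Blinding) shows that visit number is known when the nightly metrics are derived.

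**The concern.** Each night combines polysomnography, two intravenous lines and blood draws every 30 minutes. Sleeping heart rate could plausibly drift as participants get used to this. In a crossover, such drift enters every drug-minus-placebo difference, with a sign set by which came first. A paired t-test has nowhere to put it. If the sequences are equal in number, the drift cancels from the mean but inflates the error term. If they are unequal, part of it is counted as drug effect.

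Unequal numbers are plausible. The SAP allows for 20% dropout, study drug may be withheld for low blood pressure or heart rate, and inadequate nights may be repeated later. Planned power is only 80%, and at N = 16 it is reached only with a one-sided test, so there is little to spare.

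**Working it through.** **Inputs.** From the SAP (Sample size): target reduction 6.2 beats/min, SD 9.2, one-sided 0.05, power 80%, 16 evaluable. The SAP prints 9.2 as the SD of heart rate on placebo. It is used here as the SD of the paired difference because that reproduces the stated N. Assumed: period effect π of 0 to 4 beats/min, since the documents give none.

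**The plan's own figure.** Paired t-test, noncentral t, n − 1 degrees of freedom: power is 0.798 at n = 15 and 0.823 at n = 16. The stated 16 is reproduced.

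**Model.** Let D be the reduction on drug relative to placebo, τ the drug effect, and π the fall in heart rate from the earlier to the later of the two nights. Then D = τ + π when drug comes second and D = τ − π when it comes first. The mean of D has expectation τ + π(n₁ − n₂)/(n₁ + n₂), where n₁ counts participants with drug second.

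**Equal sequences (8:8).** The bias is zero, but the expected sample variance of D becomes 9.2² + π²·16/15. At π = 4 that is 84.64 + 17.07 = 101.71, an apparent SD of 10.1 instead of 9.2. Simulated results:

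| π | Power, paired t | Power, adjusted | One-sided error, paired t |
|---|---|---|---|
| 0 | 82% | 82% | 5.0% |
| 1 | 82% | 82% | 4.9% |
| 2 | 81% | 82% | 4.6% |
| 3 | 80% | 82% | 4.2% |
| 4 | 78% | 82% | 3.7% |

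**Unequal sequences (10:6).** Bias = π(10 − 6)/16 = π/4, which is 0.25, 0.50, 0.75 and 1.00 beats/min at π = 1, 2, 3 and 4. The value at 3 is 0.75/6.2 = 12% of the target. The one-sided error of the paired t-test is:
- drift favouring drug: 6.0%, 7.0%, 7.9% and 8.6% at π = 1, 2, 3 and 4;
- drift opposing drug, π = 3: 2.1%, with power 70% against 80% adjusted.

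**Averaged over allocation.** If each participant's order is an independent coin toss (an assumption), 8:8 occurs in 20% of trials of 16, and 10:6 or worse, in either direction, in 45%. Averaged over all splits, the paired t-test has zero bias, error of 5.0% and power of 82%, 79% and 73% at π = 0, 3 and 5.

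**Cost of adjusting when π = 0, two visit levels.** The adjusted estimate is the mean of the two sequence means. Its variance is (9.2²/4)(1/n₁ + 1/n₂) with 14 degrees of freedom.
- 8:8: 21.16 × 0.250 = 5.29, SE 2.30, power 82.0% (against 82.3%).
- 10:6: 21.16 × 0.267 = 5.64, SE 2.38, power 80%.
- 12:4: 21.16 × 0.333 = 7.05, SE 2.66, power 72%.

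**Three visit levels.** If drug and placebo can fall on any two of three visits, there are six orders and the visit term takes two degrees of freedom, leaving 13. With simple random order and π = 0, average adjusted power is about 76% to 77%. If the orders are balanced, so that the SE stays at 9.2/4 = 2.30, it is about 82%. Most of the loss therefore comes from imbalance and little from the extra degree of freedom.

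**The case against.** A reader might infer that the primary test is biased, or that its true false-positive rate is 8%. The documents do not support that. Because order is randomised, the paired t-test is unbiased and holds its level on average. The 8% applies only after a split such as 10:6 has occurred and the drift happens to favour drug. The same split is as likely to make the test conservative, so under simple randomisation the chance of a 10:6-or-worse split in the harmful direction is about 45%/2 = 23%. Balanced blocks are not ruled out, since the allocation method is not stated.

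The size is also open. At 1 to 2 beats/min with equal sequences the loss is about one point of power or less, and 4 beats/min would be 65% of the target effect (4/6.2). If the pre-sleep procedures describe the design correctly, the first laboratory night falls outside the drug comparison, and with it much of any first-night adaptation.

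Adjustment is not free either. Averaging the two-level power over coin-toss splits gives about 80%, against 82% unadjusted when there is no period effect and 79% unadjusted at 3 beats/min. On average power alone, the gain is small.

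All of this stands, and it limits the point. It does not remove it: one realised split will be analysed, its imbalance will be known, and the plan has no way to allow for it.

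**Conclusion.** The omission is real and is not made good elsewhere in either document. Its consequence is moderate and conditional: a few points of power with balanced sequences, and an estimate that leans by π(n₁ − n₂)/(n₁ + n₂), in either direction, when they are unbalanced. General bias or general inflation of the type I error is not shown. The figures rest on an assumed period effect of 1 to 4 beats/min, N = 16, and 9.2 as the SD of differences. If that SD is smaller, the same drift weighs more against the noise: at SD 6, 10:6 and 3 beats/min, the one-sided error is about 9% or 1%, depending on direction.

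The strongest reasons to act are that the result should not depend on a known imbalance, and that the choice between adjusted and unadjusted analysis should be fixed before unblinding.

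**What to change.** In the SAP's Analysis paragraph, replace the paired t-test with a linear model for nightly median heart rate, with drug and visit number as fixed factors and subject as block. Use the same terms for the secondary outcomes and add visit number to the mixed models in both documents.

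Reconcile the protocol's Study overview with its pre-sleep procedures, so that it is clear whether the drug comparison spans two visits or three. With two, the model is equivalent to the mean of the two sequence-specific differences and costs one degree of freedom. With three, that shortcut does not apply and visit needs three levels. State how the order is allocated and whether it is balanced, because the cost of adjustment depends mainly on that.

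No new data are needed, since visit number is already recorded. The price is a few sentences of text and, if there is no period effect, the power losses set out in the working: negligible when sequences are balanced, and larger as they become uneven.
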